## **Study Protocol**

*Treatments Procedures:*

*C-RFA Procedure (Procedure as performed as standard of care clinical practice)*

During the C-RFA procedure, the participant will be positioned prone on a fluoroscopy table. Sterile precautions, including sterile preparation, drapes, and gloves, will be undertaken. A pre-procedure time-out will be performed. Vital signs will be recorded as per usual care for sedation procedures. Patients may be mildly sedated during the procedure, using intravenous midazolam and /or fentanyl. An C-RFA electrode – Coolief® Cooled Radiofrequency Kit (Halyard Health Inc, Alpharetta, GA), will be placed at the junction of the transverse process and the superior articular process in an ipsilateral oblique fluoroscopic view, touching bone, but then with

subsequent withdrawal of the stylet, allowing a 2 mm gap between the electrode tip and the base of the superior articular process given forward projection of the cooled lesion. Appropriate positioning will be confirmed in oblique, anterior-posterior, and lateral fluoroscopic views, as is shown in the below figures per manufacturer guidelines:

Motor testing may be performed at each of the MBNs per physician discretion. Sensory testing is not required, as this technique has been shown to have no influence on treatment outcomes. After appropriate electrode positioning, 1-4 mL of 1-4% lidocaine might need to be used at a given medial branch nerve in order to effectively anesthetize it before lesioning (standard of care range). This is done through an introducer needle for anesthesia during the ablation. The C-RFA lesions will be performed by using the typical C-RFA protocol with lesions performed with the RFA generator (generator is pre-programmed). Once the procedure is completed, all needles will be removed. Following ablation, 0.25-1 mL of 0.25 -0.5% bupivacaine will be injected at each medial branch nerve to provide post procedure analgesia. No corticosteroids will be injected.

For bilateral low back pain, a maximum of 4 facet joints (two on each side) will be denervated by lesioning of up to 6 MBNs. For unilateral low back pain, up to 3 facet joints will be denervated by lesioning up to 4 MBNs.

#### *FJI Procedure (Procedure as performed as standard of care clinical practice)*

During the C-RFA procedure, the participant will be positioned prone on a fluoroscopy table. Sterile precautions, including sterile preparation, drapes, and gloves, will be undertaken.

Using an oblique fluoroscopic view, the image intensifier will be rotated to optimize the posterior joint space opening. A spinal needle will be advanced under fluoroscopic guidance to enter the posterior joint space. The needle position will be confirmed in both AP and oblique views. Approximately 0.2-1 mL of iodinated contrast medium will be injected to confirm intra-articular placement and no vascular uptake. The injection will be then completed with 0.5 mL of 40mg/mL Kenalog and 0.5 mL of 1-4% preservative-free lidocaine. This technique will be repeated for each facet joint injected.

For bilateral low back pain, a maximum of 4 facet joints (two on each side) will be injected. For unilateral low back pain, up to 3 facet joints will be injected.

*Group Assignments:*

Patients will be randomly assigned to the two treatment groups (C-RFA vs. FJI) at a 1:1 ratio. Participants who reported 50% or more relief of their usual pain (NPRS score compared to baseline) at the 3-month follow-up time point and who subsequently experience a treatment effect that diminishes by > 50% will be offered a repeat procedure. Duration of relief will be considered the time from the provision of the treatment procedure until the participant returns to 50% of their pre-treatment level of pain as reported during scheduled follow-up, or when a repeat treatment procedure is requested and performed.

*Crossover:*

Any time after the 3-month follow-up, any participant who has not obtained adequate pain relief can ask to cross over to alternative treatment group. In doing so, a new 2-year follow-up will begin for this participant who is now placed in the alternative treatment group for the long-term, as-treated outcomes analysis.

*Co-interventions:*

Patients are allowed to receive usual care, including co-interventions, as deemed necessary by the treating physician. Treatments related to the participant's spine condition will be reported on the ancillary treatment log.

*Primary Outcomes:*

The primary outcome for the randomized trial is the proportion of responders, defined by a reduction in NPRS score  $\geq 50\%$  at the 3-month follow-up.

*Secondary Outcomes:*

1. Physical function (ODI and PF CAT)
2. Global function (Global-10)
3. Analgesic use (MQS III score)
4. Global impression of change (PGIC)
5. Adverse events (Specifically only: spinal infection, epidural hematoma, and neurological damages to the spinal nerve root(s) at the treated level(s))

*Blinding:*

Participants cannot be realistically blinded to their intervention. However, all assessors will be independent and blinded. Participants will remain in their allocated groups throughout the study unless they meet the criteria for crossover treatment. In order to provide an unbiased assessment, the treating physician will be different from the outcome assessor, a trained research assistant.

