#### **1.3 Specific Aims:**

1. Determine the proportion of patients with a successful response (defined as 50% or greater improvement in index pain) to lumbar MBN C-RFA versus facet joint injection of corticosteroid at 3 months, and the duration of relief up to 2 years.
2. Evaluate the functional improvement observed in both groups, as assessed by the Oswestry Disability Index (ODI), the PROMIS Physical Function CAT (PF-CAT), and the Patient Global Impression of Change (PGIC); determine the correlation between reduction in pain and improvement in function, as well as the correlation between the

ODI and the PF-CAT in this specific population, to both the anchor score (PGIC) as well as to each other (ODI vs. PF-CAT).

4. Evaluate changes in opioid and non-opioid analgesic use in both groups, as assessed by the conversions to daily morphine equivalent use and Medication Quantification Scale III score.
5. Evaluate differences in the proportion of patients with a successful treatment response in those who reported 100% relief from dual comparative diagnostic lumbar MBN blocks relative to those with at least 80% improvement but less than 100% relief from the dual comparative blocks.
5. Report immediate, short-term, and long-term adverse effects, using a standardized survey that includes a comprehensive query of known adverse events associated with systemic steroid effects.

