## **Study Timeline**

### *Baseline:*

Participants who meet inclusion and exclusion criteria will be enrolled into the study after consenting to and before receiving treatment. The baseline examination and all baseline questionnaires will be completed within 8 weeks before the index study treatment procedure (facet joint steroid injection or medial branch radiofrequency ablation) as time is needed to obtain insurance authorization for all study procedures in the present study (all procedures in this

study represent usual care procedures: medial branch blocks, facet joint injections, and medial branch radiofrequency ablation).

*Follow-up:*

Routine scheduled follow-up will occur at 1 month (+/- 2 weeks), 3 months (+/- 4 weeks), 6 months (+/- 6 weeks), 12 months (+/- 3 months), and 24 months (+/- 3 months), at which times all follow-up measures will be obtained.

The 3-month follow-up will serve as the time point for the primary outcome analysis of the randomized trial and an intention-to-treat analysis will be used to evaluate for differences in outcomes between the two groups. The 3-month time point provides a reasonable timeframe to evaluate the clinical effects of the lumbar MBN C-RFA while also providing a humane timeframe for crossover to active treatment in those randomized to usual treatment. All subsequent follow-up periods are intended to evaluate long-term clinical outcomes of lumbar MBN C-RFA and will be evaluated with an as-treated analysis.

The study start date and the outcome assessment timeline will begin at the date of the participant's initial facet-targeted treatment. After 3 months, patients who have failed treatment (not meeting criteria for success, as described above) can be offered alternative treatment. Those who cross-over will be considered treatment failures of the original treatment, by definition, and continue on the regular follow-up schedule. A new 2-year follow-up period will begin upon cross-over.

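### The duration-of-relief rule ends relief at a score the plan counts as success, and it mixes visit dates with procedure dates in one survival analysis

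*Combined protocol and SAP*

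**What the plan says.** Section 1.3 sets as part of Aim 1 the proportion with success, "defined as 50% or greater improvement in index pain", at 3 months, "and the duration of relief up to 2 years". The Primary Outcomes paragraph also includes a reduction of exactly 50% in its responder definition.

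The Group Assignments paragraph (section 3.0, Study Protocol) gives two ways for relief to end. One is by score: relief runs "until the participant returns to 50% of their pre-treatment level of pain as reported during scheduled follow-up". The other is by procedure: "or when a repeat treatment procedure is requested and performed". The same paragraph says that month-3 responders who "subsequently experience a treatment effect that diminishes by > 50% will be offered a repeat procedure".

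Under Study Timeline, the visits from month 3 on are at 3, 6, 12 and 24 months, with windows of 4 weeks, 6 weeks, 3 months and 3 months. Loss of effect after month 3 may occur at any time, between visits included. On crossover the timeline says: "Those who cross-over will be considered treatment failures of the original treatment, by definition". It adds: "A new 2-year follow-up period will begin upon cross-over".

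The Data Analysis section announces a survival analysis of treatment benefit. It names no event date, no test and no method for losses known only to lie between two visits.

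**The concern.** Two faults sit in one sentence. First, a participant with pain 8 at baseline, 2 at month 3 and 4 at month 6 still meets the 50% criterion and has also lost relief. Second, a loss found by score carries the date of the next scheduled visit, possibly many months after it happened, while a loss followed by a repeat carries the procedure date.

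If both kinds of date enter one survival curve, recorded duration depends on how often participants ask for repeats as well as on how long relief lasts. Participants are not blinded, so that habit could differ between arms. At stake are the duration part of Aim 1 and the long-term survival comparison.

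**Working it through.** **Design figure.** The plan gives no figure for duration. Its one computed figure is 39 per group for 80% vs 50%. With mean proportion 0.65, n = [1.960 × √(2 × 0.65 × 0.35) + 0.842 × √(0.16 + 0.25)]² / 0.30² = (1.322 + 0.539)² / 0.09 = 38.5, so 39. This reproduces, and nothing below changes it.

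**Boundary.** Let b be baseline NPRS and f follow-up NPRS. Success is (b − f)/b ≥ 0.5, that is f ≤ b/2. Relief ends when f comes back to b/2. Both hold at f = b/2. The inclusion criteria require b of at least 5, so whole-number scores give 6/3, 8/4 and 10/5; odd baselines have no overlap.

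The frequency depends on the scale step, which the plan does not state. The assumptions are mean relief of 50% to 65%, SD 25 to 30 points, decline of 1 to 3 points of relief per month, and visit noise SD 10 to 20 points. Among those above 50% relief at month 3, a later visit at exactly 50% changes loss date or status in 17% to 27% (whole numbers), 9% to 15% (half points) or 2% to 4% (steps of 0.1).

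**Repeat offer against endpoint.** Let m be month-3 pain, and read the offer as more than half of the month-3 reduction being lost. The offer level is then above (b + m)/2, the endpoint is b/2, and the gap is m/2. For 8 to 2, the offer level is above 5 and the endpoint is 4. For 8 to 4 they are above 6 and 4.

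**Lateness of visit dates.** Assume loss at 3 + X months with X exponential, rate λ = ln 2/(M − 3) for true median M, and detection at the next nominal visit. Measured from month 3, the intervals (a, c) are (0, 3), (3, 9) and (9, 21). Each contributes (c − a)e^(−λa) − (e^(−λa) − e^(−λc))/λ.

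For M = 10: 1/λ = 10.10, and e^(−λt) = 0.743, 0.410 and 0.125 at t = 3, 9 and 21.

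- (0, 3): 3 − 0.257 × 10.10 = 0.40
- (3, 9): 6 × 0.743 − 0.333 × 10.10 = 1.10
- (9, 21): 12 × 0.410 − 0.285 × 10.10 = 2.04

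The sum, 3.54, divided by the 0.875 who lose relief by month 24 gives 4.05 months. For medians of 6, 8, 10, 12, 15 and 18 months the result is 3.23, 3.79, 4.05, 4.18, 4.29 and 4.35. A loss dated by a repeat planned 1 to 2 months later, or by the visit if that comes first, is 0.9 to 1.7 months late on average.

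**Comparison between arms.** Simulation with no true difference: month-3 responders only, 135/2 × 0.80 = 54 and 135/2 × 0.50 = 34; the stated share of losses is dated by a repeat after the stated delay, or by the visit if earlier; log-rank test at 0.05 (my choice, since the plan names none). False-positive rates:

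| True median | Repeating, by arm | 1-month delay | 2-month | 3-month |
|---|---|---|---|---|
| 10 months | 50% / 50% | 5.7% | 5.9% | – |
| 10 months | 50% / 40% | 5.6% | 5.8% | – |
| 10 months | 50% / 20% | 8.4% | 7.6% | 6.8% |
| 10 months | 50% / 10% | 12.7% | 10.1% | 8.6% |
| 6 months | 50% / 40% | 6.0% | 6.4% | – |
| 6 months | 50% / 20% | 16.8% | 12.5% | 10.2% |
| 6 months | 50% / 10% | 27.0% | 20.1% | 14.4% |

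Repeat runs moved the entries by about one percentage point. At 50% / 40% with a 3-month delay the rate is 6.2% to 6.5%. An intermediate gap, 50% / 30% at median 10, gives 7.0%. At median 18 every case lies between 5.0% and 6.3%. With every event assigned to its visit interval, the rate stays at 4% to 6% in all cases run.

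**The case against.** Most of the case on the other side concerns reach, and much of it stands.

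- **Crossover looks unhandled, but mostly is not.** A reader might infer that crossovers fall outside the rule. The timeline makes them failures of the original treatment. Those who had not met the success criterion at month 3 already had pain above half of baseline then, so the score rule dates them. Only crossover after an initial response lacks an event date, most visibly in the as-treated survival analysis.
- **Striking medians.** With nominal visit days and no repeats, true medians of 7 and 11 months both read 12. With visits spread over half or all of the windows they read about 11 and 13 to 15. A true median of 12 reads 24 if all losses are visit-dated, but 12.5 to 14.1 if 25% to 75% are dated by a repeat 0.5 to 2 months after loss. A general claim that reported medians will hide differences is not supported.
- **Short delays drive the highest rates.** If repeats are offered at a worse pain level than the endpoint, they come later, and the timeline allows up to 8 weeks for insurance authorization before the index procedure. This is why delays up to 3 months are shown. The excess shrinks but does not vanish.
- **Population.** The plan does not restrict duration to month-3 responders. The simulated rates do not carry over to a comparison of all randomised participants.
- **The boundary is a matter of < against ≤.** It applies equally to both arms, and no bias between arms is shown from it. The responder definition is also tied to month 3, so applying it at month 6 extends it. The contradiction in the level remains.
- **A care rule need not match an endpoint.** That is correct. Here, though, the repeat procedure is itself one of the two events ending relief, so the plan should state the relation.

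**Conclusion.** The point holds in limited form. Read literally, the rule gives one score two opposite meanings, and it dates score-based losses about 3 to 4 months late on average for true medians of 6 to 18 months. Neither result needs any difference between arms.

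A reader might go further and infer that the between-arm test is generally biased. The documents do not support that. They give no repeat, crossover or duration rates, and with equal or similar repeat rates the error is about 5% to 6%. It becomes material only with a sharp imbalance (50% vs 10% to 20%) and fairly early loss: about 7% to 13% at a 10-month median and 10% to 28% at a 6-month median, for delays of 1 to 3 months. All of this assumes exponential loss among month-3 responders.

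Nor does the fault reach the 3-month responder comparison or the sample size. Duration is in Aim 1 but not among the listed primary or secondary outcomes. It is worth correcting because two analysts following the text could derive different durations from the same data.

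**What to change.** In the statistical section:

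1. Define loss of relief as the first report of an NPRS reduction below 50%, or a repeat or crossover procedure, whichever is first. This is the complement of the responder definition and removes the overlap.
2. Assign every event to its visit interval, including crossover after initial response, and compare the arms on grouped (discrete) times. State that crossover is an event of the original treatment in the as-treated survival analysis too.
3. Report durations as intervals. Use an interval-censored model as a sensitivity analysis. It should not lead: a Weibull version gave 4% to 8% false positives and was not tested under sharp repeat imbalance.
4. State whether the repeat-offer wording in Study Timeline and Group Assignments is separate from this endpoint, or reconcile the passages. No change to care is proposed.

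The cost is a short event definition and some loss of date precision. No extra visits, participants or data are needed.

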**Power Analysis**

In the Dreyfuss et al prospective cohort study of conventional RFA for the treatment of chronic lumbar facet joint pain, which used an identical diagnostic/selective MBN block protocol (SIS guidelines), to that of the proposed study, 87% of patients experienced at least 60% reduction in pain at 10-month follow-up. For the present power analysis, we will more conservatively estimate a success rate of 80%, using 50% relief in pain at 3 months as the definition of success.

No study to date has used dual comparative MBN blocks to select patients for facet joint injection of corticosteroid. However, Carette et al. used intra-articular injection of local anesthetic only (>50% relief considered “positive) in order to select patients for a randomized controlled trial of lumbar facet joint injection of corticosteroid versus saline. In this study, a 42% success rate was observed at 3 months. For the present power analysis, we will more conservatively estimate a success rate of 50% at 3 months, as participants will be selected by dual comparative MBN blocks rather than only one intra-articular diagnostic injection.

Given that the primary analysis will be categorical in nature (comparison of the proportion of responders), with an alpha level of 0.05 and a power of 0.80, 39 participants would be needed in each group (total 78 participants) to detect a significant difference in the proportions between the two groups (80% vs. 50%) using a chi-square test. However, in order to improve the power of the study beyond the minimally acceptable standard and to account for anticipated attrition, we propose to enroll 135 patients in the trial.

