This study is intended to monitor outcomes for 2 years following facet joint intervention. Some patients reporting relief at the 3-month follow-up may experience a return of symptoms afterwards. All patients reporting relief at the 3-month follow-up will be instructed to contact their physician if and when they experience a treatment effect that diminishes by >50%. This can occur at any time following the 3-month follow-up, including the regularly scheduled follow-up intervals. Repeating the facet intervention procedure originally assigned beyond the 3-month follow-up does not reset the follow-up schedule. Patients are also free to choose alternative therapies beyond 3 months. Patients may also develop new low back pain that is different from what is being evaluated, which will be noted.

[figure not shown]

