### **Data Analysis**

Results of the randomized comparative trial will be determined by an analysis of categorical data from the 3-month follow-up. At 3-month follow-up, prior to allowing crossover, overall treatment response rates (in the previously defined categories of failure or success) will be calculated for both treatment groups using an intention-to-treat analysis. For time periods beyond 3 months, intention-to-treat and as-treated analyses will be performed with primary reporting based on the as-treated analysis to assess the long-term effectiveness of each treatment. In the intention-to-treat analysis, participants who cross-over will be treated as treatment failures of their original group assignment. In addition, a treatment benefit survival analysis will be performed.

Subgroup analyses will be performed to assess treatment response and long-term effectiveness in patients reporting 100% relief from lumbar MBN blocks as compared with those reporting between 80% relief. Data will also be examined to identify any factors that predict treatment success and need for repeat treatment.

Secondary outcomes will be similarly evaluated. For the assessment of function and global quality of life, the proportions of those achieving and not achieving the established minimal clinically important differences (MCID) will be determined and compared between the two treatment groups at the 6-month follow-up. For long-term analysis of treatment effectiveness, an as-treated analysis will determine the proportion of participants exceeding these response thresholds. In addition to these categorical outcomes, changes in group mean scores will be measured and compared.

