### *Statistical Analysis*

Descriptive statistics and graphical displays will be used to examine the central tendency and distribution of each outcome variable. Data will be analyzed using Stata (ver. 14.2, StataCorp LLC, College Station, TX, USA). An alpha level of 0.05 and two-tailed tests will be used for all hypothesis testing.

To illustrate the demographic, radiologic, and procedural characteristics of the study sample, means and standard deviations or medians and interquartile ranges (depending on the distribution of data) will be calculated for continuous variables, and frequencies and proportions will be calculated for categorical variables. Demographic, clinical, and radiologic differences will be compared between the groups (C-RFA vs. FJI) in order to ensure that the two groups are equal in terms of observed as well as unobserved covariates other than the treatment provided to them.

In comparing groups (C-RFA vs. FJI) with regard to categorical variables, Fisher's exact tests will be used. Proportions and 95% confidence intervals will also be calculated in order to confirm that any differences between groups are truly distinguished. A proportion ratio will be calculated as the measure of the effect size. For quantitative variables, independent *t*-tests or Wilcoxon-Mann-Whitney tests will be used to compare means or medians, respectively. An effect size of *r* will be calculated to examine the magnitude of a group difference.

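### Duration of relief has no end event for non-study spine procedures, so relief regained through them is credited to the original treatment

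*Combined protocol and SAP*

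**What the plan says.** The definition stands under Group Assignments in the Study Protocol. Duration runs from the treatment procedure until pain is back at half its pre-treatment level, "as reported during scheduled follow-up, or when a repeat treatment procedure is requested and performed". Those are the only two end events.

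Other parts of the protocol bear on it:

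- **Other therapies.** Study Timeline (Follow-up): "Patients are also free to choose alternative therapies beyond 3 months". The Co-interventions paragraph also permits usual care and has treatments for the spine condition entered in the ancillary treatment log. No analysis use of the log is stated.
- **Crossover.** Study Timeline: "Those who cross-over will be considered treatment failures of the original treatment, by definition, and continue on the regular follow-up schedule". A new 2-year follow-up then starts. The Crossover paragraph places the participant in the alternative group for the long-term as-treated analysis. Data Analysis counts crossovers as failures of the original group in the intention-to-treat analysis and makes as-treated the primary report beyond 3 months.
- **Survival analysis.** Data Analysis: "In addition, a treatment benefit survival analysis will be performed". Its event and censoring are not defined.
- **Visits after 3 months.** 6, 12 and 24 months.

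**The concern.** The duration rule reads pain at scheduled visits and is otherwise interrupted only by a repeat of the assigned procedure. A participant who loses relief between visits and regains it through a different, non-study procedure meets neither condition. The rule then records unbroken benefit, although the later part of that relief came from something else.

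Duration of relief up to 2 years is part of Aim 1 (section 1.3). It is also the only definition in the document that the treatment-benefit survival analysis could draw on, although the plan does not make that link explicit. If the definition is used as written, participants who needed another procedure and did well on it appear among those with the longest relief.

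**Working it through.** **The plan's own figure.** The documents give no figure for duration. Their one sample-size figure is 39 per group for 80% vs 50% response, two-sided alpha 0.05, power 0.80, 1:1 allocation (Power Analysis; Statistical Analysis; Group Assignments). It reproduces with the usual formula without continuity correction:

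n = [1.960 × √(2 × 0.65 × 0.35) + 0.842 × √(0.80 × 0.20 + 0.50 × 0.50)]² / 0.30² = (1.322 + 0.539)² / 0.09 = 38.5, rounded up to 39.

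It concerns the 3-month responder rate and does not depend on the duration rule.

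**Which later treatments end relief?**

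| Later event | Ends duration (Group Assignments)? | Handled elsewhere? |
|---|---|---|
| Pain at half of baseline at a scheduled visit | Yes | – |
| Repeat of the assigned procedure | Yes | – |
| Crossover procedure | Not listed | Yes: failure of the original treatment; followed under the new treatment in the as-treated analysis. No end date given |
| Non-study spine procedure | Not listed | No: permitted and logged only |

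**Worked case (hypothetical scores, the plan's rule and visits).** Baseline NPRS is 8, so the threshold is 0.5 × 8 = 4.

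1. NPRS is 3 at 3, 6 and 12 months. Each score is below 4, so relief continues.
2. At month 14 NPRS is 7. Relief is lost, but no visit falls here.
3. At month 15 the participant has a non-study spinal procedure. This is not a listed event.
4. At month 24 NPRS is 3, again below 4.
5. Recorded duration is at least 24 months. Relief was lost at month 14, so the excess is 24 − 14 = 10 months.

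The ceiling for one participant within 24 months is 24 − 3 = 21 months. It requires relief to be lost just after the 3-month visit and other therapy to hold the score below threshold at 6, 12 and 24 months.

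**Group-level illustration (assumptions only).** The documents give no relapse rate and no uptake of other therapy. Suppose 3-month responders lose relief exponentially with median m months after month 3, and a share q of those who lose it are kept below the threshold at visits by other therapy. Then:

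- true share still relieved at 24 months: S = 2^(−21/m)
- share counted as relieved: S + q × (1 − S)

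| m | S | Counted, q = 0.10 | Counted, q = 0.30 |
|---|---|---|---|
| 6 | 8.8% | 18.0% | 36.2% |
| 12 | 29.7% | 36.8% | 50.8% |

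**Direction between arms.** Let one arm have m = 6 and the other m = 12. The true 24-month gap is 29.7 − 8.8 = 20.9 points.

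- Same q in both arms: the gap is multiplied by (1 − q), giving 18.8 points at q = 0.10 and 14.6 at q = 0.30.
- q = 0.30 in the faster-fading arm, 0.10 in the other: 36.8 − 36.2 = 0.6 points.
- q = 0.10 in the faster-fading arm, 0.30 in the other: 50.8 − 18.0 = 32.8 points.

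Both curves rise in every case, but the gap can shrink or widen.

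**The case against.** **The route is narrow.** The worked case uses the widest gap between visits. At NPRS 7 the participant has lost more than half of the effect, is told to contact the physician, and will be offered a repeat, which is a listed end event if performed. This limits how often the problem arises. It does not remove it, because the protocol expressly leaves other therapies open and contact with the physician does not itself end relief.

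**The trial is pragmatic.** Counting relief regardless of co-intervention is a recognised choice. The plan has not made that choice consistently, though: a repeat procedure ends relief and a crossover is a failure. A non-study procedure for the same pain is the exception to the plan's own logic.

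**Stakes are limited.** Duration is not among the listed primary or secondary outcomes, and the 3-month primary analysis does not use it. That stands. Duration is nevertheless named in Aim 1.

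**Stronger readings that the documents do not support:**

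- A reader might infer that relief after crossover is also credited to the original treatment, since the duration sentence omits crossover and crossovers stay on the regular schedule. The Study Timeline, Crossover and Data Analysis text rule this out: crossovers are failures of the original treatment, and their as-treated follow-up moves to the new one. What is missing is a date. In the worked case, had the month-15 procedure been a crossover, original relief could be dated to the last relieved visit (12), the request, or the procedure (15).
- A reader might infer that the faster-fading arm must gain more. That follows if q is equal in both arms, which nothing in the documents establishes.

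**Conclusion.** The point holds for non-study spine procedures. Applied as written, the duration rule credits the original treatment with relief that another procedure produced, so duration of relief is overstated, as is any survival analysis built on it. For crossovers the gap is confined to the missing end date.

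For an individual the excess is 10 months in the worked case and at most 21 months within the 24-month schedule. At group level neither the size nor the direction between arms can be computed; the percentages above rest wholly on assumed values of m and q. That the survival analysis will use this definition is an inference, because Data Analysis does not say so. The sample size and the 3-month primary comparison are untouched. The definition should be settled before durations are analysed, but the trial's main conclusion does not depend on it.

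**What to change.** Amend the duration definition under Group Assignments and the matching text in Data Analysis, for analysis only:

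1. End duration of relief at the earliest of: the plan's existing pain-level loss; a repeat procedure; the crossover procedure; or the first non-study lumbar injection, ablation or surgery for the index pain recorded in the ancillary treatment log.
2. Disregard NPRS scores after that date for this endpoint.
3. State that this is the event definition of the treatment-benefit survival analysis.
4. Report the current two-event rule as a sensitivity analysis.

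**Cost.** This is a wording change plus use of a log that the trial already plans to keep. The documents do not say that the log records dates or the pain treated, so entries must carry dates and be classed as index-pain procedures or not. Reported durations will be shorter. Relief from medication or physical therapy is still not separated out, so the problem is reduced, not eliminated. No participant's access to treatment changes.
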